9.3. Statistical methods

9.3.1. Subjects disposition

The study report will contain the number of subjects enrolled (signed the ICF), the number of subjects randomized, the number and proportion of the subjects who completed the study per Protocol, the number and proportion of the subjects who withdrew early after randomization specifying the reasons. The number of screening failures will also be added specifying the reasons.

9.3.2. Demographic and other baseline characteristics

Demographic and other baseline characteristics including age, gender, race, anthropometric characteristics, medical history (time from STEMI debut) and other ones will be presented descriptively by treatment groups for FAS population. All data concerning demographic and other baseline characteristics will also be presented as lists. Analysis of group comparability by demographic and other baseline characteristics will be done.

9.3.3. Efficacy analysis

9.3.3.1. *Analysis of primary endpoint*

Primary endpoint is hsCRP area under curve (AUC) from Day 1 (baseline) until Day 14 [Visit 1 Day 1 – Visit 3 Day 14].

The following hypotheses will be tested for each RPH-104 dose level:

Null hypothesis H0: difference between mean $AUC_{1-14\text{ days}}$ CRP in RPH-104 group and mean $AUC_{1-14\text{ days}}$ CRP in placebo group is equal to 0.

Two-sided alternative hypothesis H1: difference between mean $AUC_{1-14\text{ days}}$ CRP in RPH-104 group and mean $AUC_{1-14\text{ days}}$ CRP in placebo group is different from 0.

Individual $AUC_{1-14\text{ days}}$ CRP values will be calculated using trapezoidal method. Mean $AUC_{1-14\text{ days}}$ CRP value will be compared between RPH-104 and placebo groups using analysis of variance ANOVA. Mean AUC values for RPH-104 80 mg, RPH-104 160 mg and placebo groups, differences in mean values and relevant two-sided 95% confidence intervals (CI) and well as p -values will be presented.

All hsCRP concentration values by study visits will also be presented as lists.

9.3.3.2. *Analysis of secondary endpoints*

- hsCRP area under curve (AUC) from Day 1 (baseline) until Day 28 [Visit 1 Day 1 – Visit 4 Day 28].
- BNP area under curve (AUC) from Day 1 (baseline) until Day 28 [Visit 1 Day 1 – Visit 4 Day 28].
- NT-pro-BNP area under curve (AUC) from Day 1 (baseline) until Day 28 [Visit 1 Day 1 – Visit 4 Day 28].

Analysis will be done similar to the analysis of the primary endpoint described above.

- Incidence of fatal outcomes (cardiac and non-cardiac) during 12-month follow-up period [Visit 1 Day 1 – Visit 6 Day 365].
- Incidence of hospitalizations due to HF or other cardiac reasons not associated with HF, or due to non-cardiac reasons during 12-month follow-up period [Visit 1 Day 1 – Visit 6 Day 365].
- Incidence of new cases of HF (defined as hospitalization due to HF or new onset of HF) during 12-month follow-up period [Visit 1 Day 1 – Visit 6 Day 365].
- Incidence of “fatal outcome (due to any reason) or hospitalization due to HF or new onset of HF” during 12-month follow-up period [Visit 1 Day 1 – Visit 6 Day 365].
- Incidence of “fatal outcome (due to any reason) or hospitalization due to HF” during 12-month follow-up period [Visit 1 Day 1 – Visit 6 Day 365].

The number and proportions of subjects (of the number of FAS subjects and valid %) with fatal outcomes, subjects with hospitalizations and subjects with new cases of HF will be presented by treatment groups. Intergroup comparisons will be performed using exact Fisher's test.

- Changes in levels of brain natriuretic peptide (BNP, NT-pro-BNP) during 12-month follow-up period compared to baseline [Visit 1 Day 1 – Visit 6 Day 365].

Changes in BNP, NT-pro-BNP levels will be presented by descriptive statistics by the study visits and treatment groups. Changes relative to baseline will be calculated for each visit.

Comparison of changes between the treatment groups after the treatment initiation, as well as the comparison of mean changes in BNP, NT-pro-BNP levels by Visits will be performed using a basic linear mixed model with the inclusion of the baseline as a covariate and the therapy group as a factor.

CONFIDENTIAL

Translation dated 27-Oct-2021

based on Russian Version 4.0 dated 02-Oct-2021

Page 64 of 98

- Changes in structural and functional echocardiographic parameters after 12 months from the baseline [Visit 1 Day 1 - Visit 6 Day 365].

The parameters will be analyzed similar to the analysis of changes in brain natriuretic peptide level described above.

In case of significant deviations from the normal data distribution, data transformation (logarithmic or other) can be used. In case of using transformations, the relevant descriptive statistics will also include a geometric mean value.

9.3.3.3. *Analysis of exploratory endpoints*

- Changes in concomitant therapy [Visit 1 Day 1 – Visit 6 Day 365].

Number and proportion of subjects (of the number of FAS-subjects and valid %) with changes in the prescribed concomitant therapy with their causes will be presented by treatment groups.

- Interaction between STEMI outcomes and peculiarities of coronary bed lesion based on baseline CAG results [Visit 1 Day 1 – Visit 6 Day 365].

Detailed description of assessment methods will be presented in the SAP.

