4.3.4.1. Visit 1 (Day 1)

Visit 1 (Day 1) includes screening, randomization and administration of the study products.

Before any study-related procedures are performed, the study nature and study-related potential risks should be explained to all study subjects and they should provide their informed consent. After informed consent is obtained, the following procedures will be carried out:

- collection of medical history;
- recording previous and concomitant therapy;
- collection of demographic data;
- recording 12-lead ECG results on which STEMI diagnosis was based

CONFIDENTIAL

Translation dated 27-Oct-2021

based on Russian Version 4.0 dated 02-Oct-2021

Page 41 of 98

- recording CAG results;
- evaluation of vital signs (BP, HR, RR, body temperature);
- physical examination;
- body weight measurement (using hospital bed, if available);
- determination of absolute neutrophil count (in local laboratory);
- urine pregnancy test for females with childbearing potential (test strips);
- blood collection for hematology and blood chemistry, determination of hsCRP, BNP and NT-pro-BNP;
- Echo-CG (this procedure is permitted to be done within 24 hours from the moment of randomization);
- evaluation of inclusion/exclusion criteria.

After the above-mentioned procedures if the subject meets selection criteria, the following procedures will be carried out:

- randomization;
- administration of the study product (must be done within 3 hours after the randomization);
- recording AE and SAE;
- recording concomitant therapy.

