4.5. Subjectivity minimization measures

4.5.1. Randomization

The subjects will be randomized in 1:1:1 ratio without stratification into one of treatment groups - RPH-104 80 mg, RPH-104 160 mg or placebo based on randomization scheme prepared using the relevant software by the responsible study statistician. Distribution will be made using block, non-adaptive, centralized randomization using Interactive Web Response System (IWRS).

At Visit 1 after eligibility of the patient is confirmed by the authorized blinded investigator, the unblinded investigator will perform randomization using the IWRS and obtain information about the patient's randomization number and assigned therapy group.

Detailed information on IWRS system will be presented in an individual IWRS manual kept in Trial Master File (TMF) and in each Investigator Site File (ISF).

The unblinded researcher will keep a register linking the screening and randomization numbers of study participants and therapy groups. Access to these registers for blinded employees will be limited.

Study participant randomization number may not be changed during the study. Distribution of the subject to a treatment group may not be changed during the study.

If the subject decides to refuse to participate or withdraw from the study for any reason, his/her randomization number may not be re-used.

Randomization scheme and identification of each subject will be added to the study report.

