7.2. Methods and terms of evaluation, reporting and analysis of efficacy parameters

Periodicity of the procedures and assessments is also provided in Schedule of visits and procedures (see Table 1).

Blood sampling to determine concentration of hsCRP and level of brain natriuretic peptide (BNP, NT-pro-BNP) will be made at Visit 1 Day 1 (at baseline), Visit 2 (Day 3), Visit 3 (Day 14±3) and Visit 4 (Day 28±3) of the study. In addition, blood sampling to determine level of brain natriuretic peptide (BNP, NT-pro-BNP) will be made at Visit 6 (Month 12±2 weeks) of the study. Concentration of hsCRP and level of brain natriuretic peptide (BNP, NT-pro-BNP) will be determined in central laboratory.

Throughout the clinical study, the investigator will follow the subjects to evaluate and record cardiovascular and other outcomes (fatal outcomes, hospitalizations¹, new HF) based on the current clinical recommendations and terminological criteria "2017 Cardiovascular and Stroke Endpoint Definitions for Clinical Trials" (Hicks K.A. et al., 2018) (see Attachment 1).

Echo-CG will be carried out at Visit 1 (Day 1) (this procedure is permitted to be done within 24 hours from the moment of randomization), Visit 4 (Day 28±3) and Visit 6 (Month 12±2 weeks) by qualified personnel of the study site using relevant diagnostic equipment. Measurements will be carried out in accordance with the internal document on the interpretation of echo-CG findings. Echo-CG parameters assessed during the study are described in detail in the Statistical Analysis Plan. Given that Echo-CG is an operator-dependent technique, assessment and recording echo-CG results will be centralized.

The following information will be collected upon dose change, dosing scheme modification or product discontinuation in concomitant therapy: date of change, description of change (discontinuation, dose escalation, dose reduction, switch to another product of another group), cause of changes (improved condition, aggravated condition, adverse events/adverse reactions associated with the study product).

8. Safety evaluation

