9.2. Selection of data for the analysis

Statistical analysis will be conducted in the following study sets:

Full analysis set (FAS) for the efficacy analysis

Full analysis set (FAS) for efficacy analysis will include all randomized subjects who received the study products and underwent at least one hsCRP measurement after administration of the study products. This set is the main population for efficacy assessment.

Per Protocol Set (PPS)

ProtocolAll FAS subjects without important Protocol deviations affecting assessment of the primary efficacy parameter. Such Protocol deviations will be defined before breaking the blind in a blinded data review. This set is supplementary population for efficacy assessment.

Safety set

All randomized patients who have received the study drugs.

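### The AUC endpoints are compared by ANOVA with no covariate named; adjusting each AUC for the marker's own Day 1 value is a likely, not guaranteed, precision gain at almost no cost

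*Combined protocol and SAP*

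**What the plan says.** For the primary endpoint, section 9.3.3.1 calculates individual hsCRP AUCs by the trapezoidal rule and says that the mean "CRP value will be compared between RPH-104 and placebo groups using analysis of variance ANOVA". It lists no covariate. For AUC to Day 28 of hsCRP, BNP and NT-pro-BNP, section 9.3.3.2 says "Analysis will be done similar to the analysis of the primary endpoint described above".

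The same section compares BNP and NT-pro-BNP change "using a basic linear mixed model with the inclusion of the baseline as a covariate and the therapy group as a factor", and for echocardiography "The parameters will be analyzed similar to the analysis of changes in brain natriuretic peptide level described above".

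The Day 1 value is a pre-treatment measurement. Section 7.2 says that sampling for the three markers "will be made at Visit 1 Day 1 (at baseline), Visit 2 (Day 3), Visit 3 (Day 14±3"), and then at Visit 4 (Day 28). Section 4.3.4.1 lists the Day 1 draw ahead of the sentence "After the above-mentioned procedures if the subject meets selection criteria, the following procedures will be carried out", which introduces randomisation and dosing. Section 4.5.1 uses no stratification factor: "The subjects will be randomized in 1:1:1 ratio without stratification into one of treatment groups".

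Section 9.1 leaves the detailed methods to a SAP whose text is not in the document supplied. Section 9.7 runs the primary and Day 28 AUC analyses once, after the last subject reaches Day 28, and does not repeat them at the final analysis.

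**The concern.** The AUC contrasts with placebo are the trial's main efficacy result. Section 2.4 says that the dose for later phases will be chosen on the risk-benefit shown in this study, and these contrasts feed into that choice. A covariate that is measured before randomisation, is already collected and is already needed to compute the AUC is left out of the model. If it is prognostic, the confidence interval for each dose is wider than the data require. The protocol uses baseline for two of these three markers in one secondary analysis and not in another, and gives no reason. Because the analysis is done only once, the model has to be settled beforehand; a covariate added after the results are seen would carry little weight.

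**Working it through.** **Inputs.** From section 9.4: placebo AUC mean 350, SD 250; standardised effect 0.80 for the lower dose, that is 0.80 × 250 = 200 AUC units; 34 per arm; two-sided alpha 0.05; 20% loss, so 34 × 0.8 = 27.2, taken as 27 per arm. Sampling on Days 1, 3, 14 and 28 is from section 7.2. The within-arm correlation ρ between Day 1 value and AUC is not in the documents and is an assumption.

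**Step 1: reproduce the stated power.** For a three-arm ANOVA the noncentrality is 0.80 × √(n/2) with 3n − 3 degrees of freedom.
- n = 34: 0.80 × √17 = 3.298, 99 df, power 90.4% (stated: above 90%).
- n = 27: 0.80 × √13.5 = 2.939, 78 df, power 82.7% (stated: above 80%).

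A two-arm t-test gives 90.2% and 82.2%. The plan's figures hold.

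**Step 2: plausible ρ from the schedule.** Trapezoid weights are 1, 6.5, 5.5 (sum 13) for Days 1, 3, 14, and 1, 6.5, 12.5, 7 (sum 27) for Days 1, 3, 14, 28. With equal SDs and a common between-visit correlation c,

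ρ = [1 + c(W − 1)] / √[(1 − c)Σw² + cW²],

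where W is the sum of the weights.
- AUC to Day 14, Σw² = 73.5. c = 0: 1/√73.5 = 0.117. c = 0.3: 4.6/√102.15 = 0.455. For c = 0.1 and 0.2, ρ is 0.241 and 0.353.
- AUC to Day 28, Σw² = 248.5. c = 0: 1/√248.5 = 0.063. c = 0.3: 8.8/√392.65 = 0.444.

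If SDs after Day 1 are three times the Day 1 SD, c = 0.1 to 0.3 gives 0.17–0.40 (Day 14) and 0.17–0.42 (Day 28). With c = 0, ρ for Day 14 falls to 1/√653.5 = 0.04.

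**Step 3: ANCOVA.** The SE is 250√(2/n) × √[(1 − ρ²)(1 + 1/(3n − 5))] with 3n − 4 df; the last factor is the cost of estimating the slope. At n = 34 the unadjusted SE is 250√(2/34) = 60.6, with a 95% CI half-width of 120.3.

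| ρ | Power, 34 per arm | CI half-width, 34 per arm | Power, 27 per arm |
|---|---|---|---|
| ANOVA | 90.4% | 120.3 | 82.7% |
| 0 | 90.1% | 120.9 | 82.2% |
| 0.12 | 90.5% | 120.1 | 82.8% |
| 0.24 | 91.7% | 117.4 | 84.4% |
| 0.35 | 93.5% | 113.2 | 86.9% |
| 0.455 | 95.4% | 107.7 | 89.9% |

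The SE is unchanged where ρ² = 1 − 1/[1 + 1/(3n − 5)], that is at ρ = 0.10 (n = 34) or 0.11 (n = 27). In simulation with normal data, the ANCOVA's type I error was 4.6–5.2%.

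**Step 4: AUC to Day 28.** Section 9.4 gives no planning effect, so only SE ratios apply. At n = 34 they are 1.003 for ρ = 0.063 and 0.90 for ρ = 0.444.

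**The case against.** The strongest reply is that nothing is wrong. Under randomisation the ANOVA is unbiased, its standard error already allows for chance baseline imbalance, the power target is met, and sections 9.4 and 9.5 call the study exploratory. All of that stands. A reader might infer that the missing covariate biases the comparison or leaves the trial short of power; the documents support neither.

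A reader might also see the baseline-adjusted change analyses as contradicting the unadjusted AUC analyses. They do not. A change score is computed from baseline by subtraction, whereas Day 1 carries only 1/13 or 1/27 of the AUC weight. Different endpoints may have different models; the contrast shows only that the sponsor already uses this device.

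The gain is not assured either. ρ is undocumented and the between-visit correlations are assumed. If visits are nearly independent there is no gain, and for AUC to Day 28 there would be a trivial loss. Inclusion criterion 4 allows randomisation up to 24 hours after symptom onset, so the Day 1 value may be an early and weak predictor. The link to dose selection is indirect: each dose is tested against placebo, and the choice also weighs safety.

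The SAP may already contain the term, and section 9.7 mentions a sensitivity analysis without describing it. The claim is therefore limited to what the protocol names. None of this makes the covariate-free model the better choice.

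**Conclusion.** The point holds as something to consider. For the primary AUC, over ρ of about 0.12 to 0.46, the gain in power runs from about 0.1 to 5 percentage points with 34 per arm (90.4% to 90.5–95.4%), and from about 0.1 to 7 points with 27 (82.7% to 82.8–89.9%). At the top of that range the interval is about 10% narrower with 34 per arm (120.3 to 107.7). The worst case, ρ = 0, costs 0.3 or 0.5 points. The case rests on this asymmetry: the possible loss is small and bounded, and the possible gain is larger, chiefly when the analysed sample shrinks to 27.

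The figures assume normal data, a common slope across arms and the between-visit correlations stated above. They are indicative only. With the planning values, a normal model puts about 8% of placebo AUCs (350/250 = 1.4 SD) and 27% of low-dose AUCs (150/250 = 0.6 SD) below zero, so skewness and the choice of scale matter.

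**What to change.** Before the analysis after Day 28, state in the protocol or SAP that each AUC is analysed by ANCOVA with treatment group as factor and that marker's own Day 1 value as covariate. Report adjusted differences in mean AUC versus placebo with 95% CIs, and keep the unadjusted ANOVA as supportive.

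Fix the scale at the same time, because section 9.3.3.2 permits transformation. If the AUC is log-transformed, enter the log Day 1 value; the contrast is then a ratio of geometric means and no longer a difference in means.

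Say also how a missing Day 1 value is handled. The full analysis set requires only that subjects are randomised and are those "who received the study products and underwent at least one hsCRP measurement after administration of the study products", so it does not guarantee a Day 1 value. An AUC that starts on Day 1 needs that value anyway, so one rule can serve both.

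The cost is wording and one degree of freedom, with no new visits or samples, and under 1 percentage point of power if the Day 1 value is not prognostic. On the untransformed scale the stated hypothesis is unchanged. If the SAP already has the term, confirming it is enough.

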9.3.4. Safety analysis

Safety analysis will be carried out on safety set.

Scope of application will be presented specifying the following variables: the number of subjects receiving RPH-104 80 mg, the number of subjects receiving RPH-104 160 mg and the number of subjects receiving placebo.

AEs will be coded using Medical Dictionary for Regulatory Activities (MedDRA). The number and percentage of the subjects with AE/SAE, overall number and percentage of recorded AE/SAE, the number and percentage of AE/SAE resulting in early withdrawal will be presented by system organ class, preferred terms and treatment groups. The data will also be generalized by the number and percentage of AEs/SAEs with various categories of causality, expectedness and severity. All AEs will be additionally presented as listings.

Quantitative safety laboratory parameters will be presented using descriptive statistics by visits and treatment groups. Changes relative to baseline and abnormal laboratory values will also be provided. The data on the number of subjects with abnormal laboratory values will be generalized for the whole study period, by visits and treatment groups. All laboratory findings will be presented as lists.

Vital signs will be presented using descriptive statistics by visits and treatment groups. Changes relative to baseline will also be presented.

9.5. Applied level of significance

Probability of type I error (two-sided level of significance) is established at 5% level for all comparisons. Due to exploratory nature of the study, adjustments for multiple comparisons are not planned.

9.6. Reporting deviations from the initial analysis plan

Deviations from the planned statistical analysis will be agreed with Sponsor and reflected in the study report.

9.7. Interim analysis

After the last subject completes 28-day follow-up period, an interim analysis of hsCRP, BNP and NT-pro-BNP will be performed after 14 and 28 days of the study. Based on this analysis, decision on the study termination will not be taken. The analysis results may be used to define the strategy for further RPH-104 development.

Population for performing an interim analysis – Full Analysis Set.

During the interim analysis the primary efficacy analysis will be performed (see section 9.3.3.1). This analysis will be performed only once and will not be repeated during the final analysis stage. Sensitivity analysis can't be done during the interim stage and will be performed during the final analysis stage.

Secondary efficacy variables (AUC from day 1 to day 28) will be derived and analysed for parameters hsCRP, BNP and NT-pro-BNP at the interim analysis stage (see section 9.3.3.2). This analysis will be performed only once and will not be repeated during the final analysis stage.

Values at visits (Day 1 – baseline, Days 3, 14 and 28) and changes from baseline (Days 3, 14 and 28) will be described for hsCRP, BNP and NT-pro-BNP parameters using descriptive statistics supported with graphics.

All individual subject's data will be kept blinded for the Sponsor and all other staff involved into the data review except unblinded statistician.

9.8. Independent study clinical outcome assessment committee

An independent study outcome assessment committee (ISOAC) will be arranged to assure reliability and quality of data on assessment of cardiovascular and other Protocol-defined outcomes as efficacy parameters. The committee will include three independent cardiologists with the relevant qualification for outcome classification according to terminology criteria 2017 Cardiovascular and Stroke Endpoint Definitions for Clinical Trials (Hicks K.A. et al., 2018) (see [Attachment 1](#)). Outcome classification will be blinded. ISOAC-defined outcome classification will be considered to be final for the purpose of the study result analysis. The committee shall convene in accordance with the approved work plan. The information on the composition, procedures and decisions of ISOAC will be included into the study report.

10. Quality control and quality assurance

10.1. General quality assurance information

Sponsor should establish relevant quality assurance and control system for the performance of this clinical study in accordance with the study Protocol, Good Clinical Practice and current regulations of the RF, EAEU and USA.

The study procedures specified in the Protocol should be followed strictly by Investigator and investigator's team members.

